At this time, the subject's socket would be fit with an activity monitor (such as the StepWatch™) to measure the use of the prosthesis and temperature sensors (such as the iButton) on the exterior of the socket to monitor the ambient temperature and on the interior of the socket/liner to monitor the intrasocket temperature. The Thermochron family of iButtons are tiny, durable data loggers that monitor time and temperature that have been used clinically and in take-home research studies in the O&P field. The StepWatch is an activity monitor/step counter that has been shown to have excellent accuracy at slower gait speeds typical of lower limb amputees. These measures would be used as reference measures to have a better understanding of the user's activity. The subject will wear their newly instrumented socket at home for 5 weeks.

The subject will be instructed to wear the new liner without the socket at home for roughly 1 hour a day for the first week (this can be accomplished during everyday tasks such as working at a desk or watching TV on the couch). This adjustment period will allow their limb to become accustomed to the experimental liner. After the one week period a research coordinator will contact the subject to check in and remind them to start wearing the experimental liner with their socket as they would with their standard everyday liner for the next 4 weeks.

During this time, the subject will be asked to give feedback on the thermal comfort and perspiration in the socket. The feedback will be obtained via a paper log on which the subject enters daily feedback on thermal comfort and perspiration over the course of the final 4 weeks. A research coordinator will be calling subjects periodically to remind them to fill out the log and answer any questions that they may have.

This visit will take up to 2 hours.

Visit 2: At the end of the month-long testing period, the subject will return to the lab for a 2nd visit. During this visit, they will be asked to complete the same QoL questionnaire given previously, but this time with respect to the experimental liner. Then, all sensors will be removed from the subject's socket and the experimental liner will be returned to the site. The staff prosthetist at the site will inspect the limb to check for any skin issues and ensure their standard everyday liner is still comfortable within their socket.

This visit will take up to 2 hours.

At the end of this visit, the subject will have completed the study.

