
8. Study Conduct

Subjects will be consented and screened for eligibility criteria by LTI over the phone. According to each site's privacy standards and with the subject's permission, identifiable information such as name, phone number, and email address, will be shared from the involved prosthetists at RISE to LTI. After being consented the subject will share their own information (mailing address, etc.) to LTI for payment. If the subject decides to participate, their usual socket will be instrumented with an activity monitor and temperature sensors. The subject will wear the instrumented usual socket home with the experimental liner for 5 weeks, then return their experimental liner and sensors back to the lab. The study will consist of a 5 week period of participants wearing the experimental liner at home and logging their comfort, activity levels, temperatures, and feedback.

Subjects may withdraw at any time by simply telling the investigators they wish to stop their participation.

If a subject withdraws from the study, the data that were collected from them can still be used, and the withdrawn subjects may be replaced with a new subject. Deviations from the protocol that increase risks for subjects will be reported to Solutions IRB and HRPO for approval prior to being implemented.

Approved study staff from Vivonics, Inc. may also be present during testing visits at LTI to provide technical support or monitor testing activities. During these visits approved study staff from Vivonics, Inc. may be in contact with the subjects.

Subjects will be compensated \$40 per hour for the in-lab visits for an estimated total of \$160 per subject. For the take-home testing, each subject will receive \$250 for the 5 weeks of wearing the experimental liner. The anticipated total to complete the study would be \$410.

9. Study Treatment

This study is not a means of providing any sort of medical treatment to its participants. The purpose of the study is to evaluate the effectiveness of the experimental liner. No drugs will be administered to the participants.

10. Evaluation of Adverse Events

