Based on past testing and data collection, no adverse events are expected. Adverse events could include discomfort or dermatological reaction due to either the experimental liner materials or socket/liner fit. These risks have been mitigated by using biocompatible materials as well as having a certified prosthetist present while the subject tests the fit of the experimental liner with their usual socket.

All unanticipated problems involving risk to subjects or others, serious adverse events related to participation in the study and subject deaths related to participation in the study will be promptly reported to Solutions IRB and HRPO. A written description of the adverse event will be stored in the study file maintained by the Principal Investigators. Also, the protocol will be reviewed in light of the adverse event to determine if modifications need to be made to prevent the event from occurring again. Major modifications to the research protocol and any modifications that could potentially increase risk to human subjects must be submitted to Solutions IRB and HRPO for approval prior to implementation.

11. Ethical Considerations

There is no direct benefit to the user. Participating in this study may potentially advance the scientific community's understanding of the effect of reducing intra-socket moisture and temperatures on the activity, comfort and quality of life of lower limb amputees.

The protocol, consent form, and recruitment flyer will require IRB review and approval. The principal investigator will be in continuous communication with the IRBs and HRPO and will forward information to the co-investigators. Subjects' participation is voluntary, and they may withdraw from participation in the study at any time by simply telling any one of the investigators that they wish to stop. The investigators may choose to terminate a subject's participation if he or she experiences discomfort or injury. In addition, participants will be given any new information which is discovered during the course of the study which may influence participants' willingness to continue the study. If they desire to do so, subjects will also have the option to discuss any concerns regarding the study activities or the investigators with an impartial staff member of the site IRB, whose duty it is to hear and review such concerns and provide advice or take any other appropriate actions.

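### No skin question is scheduled during the five weeks of home wear, so reactions that resolve before Visit 2 rely mainly on spontaneous report and may be under-recorded

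*Combined protocol and SAP*

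**What the plan says.** Section 10 identifies the foreseeable harm: "Adverse events could include discomfort or dermatological reaction due to either the experimental liner materials or socket/liner fit". It adds that no adverse events are expected.

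Section 8 sets the exposure: "The subject will wear the instrumented usual socket home with the experimental liner for 5 weeks". Under Section 7, week 1 is an adjustment period of roughly an hour a day without the socket. Normal wear with the socket follows for four weeks.

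What is collected in that time:

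- **Daily log, Section 7.** The participant "enters daily feedback on thermal comfort and perspiration over the course of the final 4 weeks".
- **Daily log, Section 8.** The five-week period is described as participants wearing the liner and "logging their comfort, activity levels, temperatures, and feedback".
- **Week-1 contact, Section 7.** "After the one week period a research coordinator will contact the subject to check in and remind them to start wearing the experimental liner" with the socket.
- **Later contacts, Section 7.** The coordinator will be "calling subjects periodically to remind them to fill out the log and answer any questions that they may have".
- **Visit 2, Section 7.** "The staff prosthetist at the site will inspect the limb to check for any skin issues". The questionnaire from Visit 1 (EuroQol-5D, DLQI and mDLQI) is repeated, this time about the experimental liner.

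Once an event is known, Section 10 requires a written account in the study file and a review of the protocol. Section 12 makes the co-investigators responsible for reporting adverse events. Section 14 lists temperature, steps, the log and the surveys, and has no summary of adverse events or skin events.

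**The concern.** The plan names a specific harm but schedules no question that would find it while it is happening. Sections 10 and 12 say what to do with an event once somebody knows of it; they do not provide a way of learning of it. Skin is also not a side issue here. Section 13 describes a prototype material with added nanoparticles in prolonged skin contact, and Section 5 says the pilot is meant to inform on quality of life in relation to skin problems.

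Two things are at stake. The investigators may hear of a developing problem later than they could have. And the record of skin reactions that this pilot hands to a larger study may be incomplete, with no means of telling afterwards how incomplete.

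**Working it through.** The plan gives no figure to reproduce on this point, so the check sets each source of information against one question: would it capture a mild skin reaction that starts and resolves before Visit 2?

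**Time covered.** Home wear is 5 weeks, or 5 × 7 = 35 days. The Section 7 log covers the final 4 weeks, or 4 × 7 = 28 days. That leaves 35 − 28 = 7 days, the first days of contact with the new material, without a stated log. Exposure in that week is light: about 7 × 1 = 7 hours. Section 8, read alone, could mean that logging runs for all five weeks. The two sections differ on this.

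**Content, source by source.**

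| Source | When | Would it capture the reaction? |
|---|---|---|
| Log (Section 7) | Weeks 2–5 | Not by design; its two topics are thermal comfort and perspiration |
| Log (Section 8) | Five-week period | Possibly, if the participant writes it under general comfort or feedback; skin is not named |
| Week-1 check-in | Once | Unknown; no skin content is stated |
| Periodic calls | Weeks 2–5, number not given | Only if the participant brings it up |
| Limb inspection | Visit 2 only | No, if it has resolved; none is stated at Visit 1 or on withdrawal |
| DLQI and mDLQI | Visits 1 and 2 | Indirectly; they score impact, not onset, type or resolution, and the plan states no recall period |

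No row is a scheduled skin question during home wear. For a reaction that resolves early, the route into the record is mainly the participant's own initiative.

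**Direction and size.** Let p be the proportion of participants who have a reaction and s the share of those reactions that are recorded. The expected recorded proportion is p × s. Because s cannot exceed 1, p × s ≤ p, so missed events can only lower the recorded proportion. The documents give neither p nor s, and no size follows from them.

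The only available scale is the weight of one participant. That is 1/12 = 8.3% of the target usable sample, or 1/16 = 6.25% of the maximum recruited (both in Section 5). These are units of measurement, not estimates of the loss.

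**The case against.** The strongest case on the other side has four parts.

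1. **Skin is asked about.** Two dermatology instruments are completed for the usual liner and again for the experimental one. This stands, and it rules out saying that skin is never asked about. It does not close the gap, because the instruments come after the exposure and do not date or describe an event.
2. **The plan is broader than Section 7's log.** The check-in is a separate contact before full wear begins, and Section 8 adds comfort and feedback. Discomfort is itself one of the adverse events that Section 10 names, so a comfort entry is relevant. This stands too. The text does not show that skin goes unmentioned, only that nothing schedules it.
3. **There is a route for reported events.** Filing, protocol review and onward reporting are all provided for. A reaction that is volunteered would be handled, so the fair wording is that a transient reaction may go unrecorded, not that it will.
4. **Some material is not visible.** The log form and call scripts are not in the text, and consent pages were removed. Instructions to report skin problems cannot be assumed, but their absence cannot be held against the plan.

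A reader might go further and infer that the liner will look safer than it is, or that a tolerance result is biased. The documents do not support this. No tolerance or reaction-rate endpoint is planned, and the stated outcomes concern quality of life, function, comfort, activity and satisfaction. Nor is there any reaction rate from which a distortion could be calculated.

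**Conclusion.** The point holds as a gap in how adverse events are found. A foreseeable harm is named, no skin question is scheduled in the 35 days of home wear, and early-resolving reactions rest mainly on spontaneous report. The consequence is possible under-recording and late knowledge. Any error runs towards too few recorded reactions, by an amount the documents cannot determine.

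This rests on reading the visible text as the full schedule. If the log form or call script already carries a skin item, the remaining need is to state it in Sections 7 and 14. For a pilot with a target of 12 usable participants this is an inexpensive improvement worth making before exposure starts, because transient reactions are hard to reconstruct afterwards. It does not invalidate the planned outcomes.

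**What to change.** - **Section 7, log.** Add one dated yes/no skin item (for example redness, itch, blister or soreness) with free text, completed daily from Visit 1 and therefore including week 1. Bring the log descriptions in Sections 7 and 8 into line.
- **Section 7, contacts.** Ask the same item at the week-1 check-in and at each periodic call, and record the answer.
- **Section 14.** List the number of participants with any skin reaction and its timing, among all who wore the liner, including those who withdrew.

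The cost is one line on a form already in use and one question in contacts already planned, with no added visit. The downside is slightly more reports to file.
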